The intervention team at each site consists of a health psychologist, a registered dietitian, and health coach (e.g. lay person who has achieved success with lifestyle modification). Together they co-facilitate group meetings of approximately 15 participants. There is an intensive phase where meetings are held weekly for 3 months and bi-weekly for 3 months. The first 3 months is aimed at initiating change, focusing primarily on food intake, eating behavior, and weight. The last 3 months is aimed at maintenance, focusing on physical activity and a variety of other strategies that enhance maintenance. A maintenance phase follows the intensive phase where participants meet on a monthly basis to check in, report on challenges and successes, and learn about a new topic of their choice.

The format for all of the sessions in the intensive phase is an ecologically valid set of activities within which old habits emerge and new habits can be explored. Participants work out together, prepare a vegetable dish

together, and eat while participating in an experiential exercise. The duration of each session is 90 minutes: physical activity (20 min), cooking demonstration (20 min), and discussion (50 min).

The maintenance phase (months 7 to 24 after randomization) consists of participant-led monthly meetings. Participants are encouraged to broaden their health network by opening maintenance sessions to members of other ELM groups at the site and participating in national ELM activities through the website. Meetings are available at least twice a month for the duration of the intervention to minimize non-attendance due to competing activities. The health psychologist and dietitian alternate in supporting the participant-led meetings.

The Self-Directed Arm

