The Self-Directed lifestyle program is intended to represent an enhanced version of what is currently available in clinical practice for patients who express an interest in using lifestyle change to manage their MetS. The current state-of-the-art in primary care for lifestyle management is the provision of evidence-based health education, featuring clear guidelines and behavioral targets, endorsed by the American Heart Association, American Diabetes Association, United States Department of Agriculture, and the Academy of Nutrition and Dietetics. Educational tip sheets are sent to participants on a monthly basis by their preferred method. Further enhancement is provided by giving all participants a Fitbit, one of the most popular wearable activity trackers available in technology today, and instructing them in how to use it to self-monitor their physical activity. An additional enhancement is provided by giving participants access to the ELM website that contains educational materials and other trial-related information.

The Self-Directed arm has been designed to serve as a clinically relevant comparator. It is intended to be the optimum status quo in medicine and technology, to which the efficacy and the cost-effectiveness of the Group-Based intervention can be compared. It has not been designed to control for attention, content, format, or other potential treatment mechanisms.

Each site has a Self-Directed Coordinator who meets with each participant post-randomization to introduce them to the components of the Self-Directed program, and train them on use of their Fitbit and the ELM website. The Self-Directed Coordinator is available, via telephone, to answer participant questions about the trial. The Coordinator calls the participants every 3 months to answer questions about the trial and to enhance protocol adherence. The Coordinator does not answer medical or behavioral questions about lifestyle change. Instead, the participant is referred back to the relevant educational sheet or the primary care physician to get such questions answered. The essential role of the Coordinator is to facilitate participant ability to adhere to the protocol and to prevent risk of drop-out.

Fidelity Monitoring

Group-Based Program Fidelity

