These visits are intended to document the impact of the treatments over time. Thus it is important that the timing of the assessments align with pivotal dates associated with intervention delivery (e.g., completion of the 6-month intensive phase, half-way through the 18-month maintenance phase, at the end of the trial at 24 months).

The timing of in-person follow-up visits is presented in the table below. This timing applies to all participants, regardless of the treatment arm to which they were assigned. The target date of first follow-up visit is one day after the date of the last meeting in the intensive phase of the Group-Based arm. The second and third follow-up visits are 9 and 18 months post-intensive phase, respectively. All follow-up visits have a 9-week window for completion that opens on the target date.

Table 1. Timing of In-Person Follow-Up Visits

Visit #	Schedule
First (Post-Intensive Intervention – PII)	Date of last group session of intensive phase (session 19)
Second (Mid-Maintenance – MM)	~9 months after intensive phase
Third (End of Treatment – EoT)	~18 months after intensive phase

The essential goals of these visits are to collect follow-up data, update/confirm contact information, monitor adverse events, and promote retention. These contacts also provide the opportunity to sustain a professional and caring relationship with the participant throughout the 2-year trial. All visits are conducted by the same staff member, whenever possible, to cultivate a relationship that can aid in retention.

Telephone Contacts

The main purpose of the telephone contacts is to ascertain vital status, obtain information on health care utilization and co-interventions, and update contact information. These contacts occur at 3 months from randomization (for the first telephone contact) and then every 3 months after the date of the last group session. There is a total of 5 telephone contacts. This schedule is the same for all participants randomized at the same time, regardless of the arm to which they were assigned. The window for completion of telephone contacts is 2 weeks before and after the target date.

Assessments

Table 2 presents the assessments completed at each trial visit.

Table 2. Assessments by trial visit and assessor		
Assessment	Frequency of Assessment B=Baseline, PII = Post-Intensive Intervention, MM = Mid-Maintenance, EoT = End-of-Treatment	Assessor RA = Research Assistant PPT = Participant
Accelerometry	B, PII, MM, EoT	RA

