Vital Status, Adverse Events, Co-Interventions	3, PII, 9, 12, MM, 18, 21, EoT	RA
Contact Info	B,3, PII, 9, 12, MM, 18, 21, EoT	RA
Five-Facet Mindfulness Questionnaire	B, PII, MM, EoT	RA
Eating Competence Questionnaire	B, PII, MM, EoT	RA
Demographics	B, PII, MM, EoT	RA
Labs (Lipid Panel, Glucose and A1c)	B, PII, MM, EoT	RA
Medical History	B, PII, MM, EoT	RA
NCI's Fruit and Vegetable Screener	B, PII, MM, EoT	RA
Food Log and Logistic Plan	B	RA
Perceived Stress Scale	B, PII, MM, EoT	RA
Depression: Patient Health Questionnaire (PHQ-8)	B, PII, MM, EoT	RA
Physical Measures (BP, HR, Waist, Weight, Height)	B, PII, MM, EoT	RA
Automatic Habits: Self-Report Habit Index	B, PII, MM, EoT	RA
Social Support for Diet and Exercise	B, PII, MM, EoT	RA
Sugar-Sweetened Beverage Intake	B, PII, MM, EoT	RA
Visit log	B, PII, MM, EoT	RA
Quality of Life: Short Form Health Survey (SF-36)	B, PII, MM, EoT	RA
Contacts with Health Network	B, PII, MM, EoT	RA
Prescription Medications	B, PII, MM, EoT	RA
MacArthur Ladder of Subjective Social Standing	B	PPT
USDA Food Security	B	RA
Treatment Credibility Questionnaire	B	PPT
Patient Preference for Each Treatment	B	RA
Program Satisfaction	EoT	PPT
Substance Use/Abuse - WHO ASSIST	B	RA

Montreal Cognitive Assessment	B	RA (if needed)
-------------------------------	---	----------------

Change of Status

The trial status of a participant refers to their level of participation in the trial. A *Participant Status Form* is completed whenever a status change occurs. All efforts are made to collect data on the primary outcome (MetS at 2 years), at the very least.

Lost-to-Follow-Up. A participant is considered “lost-to-follow-up” after missing two consecutive trial contacts without responding to messages, texts, or other forms of communication. Staff exhausts all avenues to locate the participant, including telephoning at least 10 times on different days, at varying times of day, contacting secondary contacts and the last medical provider on record, and checking online to identify new contact information. Failure of these attempts triggers a registered letter sent to the participant’s most recent address, to which non-response confirms the status as “lost-to-follow-up.”

Withdrawal from the Intervention. This status applies to a participant who no longer wants to participate in any intervention activities, but is willing to continue completing follow-up visits.

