Figure 6 presents the structure of this multi-site trial. Leadership is provided by an eight-member Steering Committee comprised of the Principal Investigators of all 5 sites, the Trial Chair, the Research Coordinating Unit Director, and the Intervention Coordinating Unit Director. Decision-making uses consensus as a primary strategy. Votes on key questions are carried by a majority. Intervention training and fidelity is overseen by the Intervention Coordinating Unit. Quality of Data transmittal is overseen by the Research Coordinating Unit. Scientific Committees guide all scientific aspects of the trial. An independent Data and Safety Monitoring Board approves the trial protocol, monitors data quality and safety, and monitors outcomes by trial arm. It makes recommendations to the investigators and the funder by providing independent reports simultaneously.

[figure not shown]

Figure 6. ELM trial organization

SAFETY MONITORING

This trial presents low risk to participants given the nature of the lifestyle interventions and the trial measurements collected. Participants are thoroughly screened prior to enrollment to ensure their ability to participate in lifestyle interventions. Nonetheless, several types of unanticipated problems and adverse events may occur and will be monitored. All potential events reported by a participant or staff member are documented using the *Adverse Events Form*. This form is submitted to the Research Coordinating Unit (RCU), which will then submit it to the Site Physician within a predetermined timeline. The Site Physician adjudicates the event following guidelines and reports back to the RCU. The RCU sends the completed adjudication form to the Chair of the Safety and Ethics Committee and Trial Chair, as described below. Summary reports are provided to the Rush IRB and the Data and Safety Monitoring Board. The Chair of the Safety and Ethics Committee can alert the Data Safety and Monitoring Board at any other time at his/her discretion.

Adverse Events

The following procedures occur dependent upon determination of the event.

- **Adverse Events** and **Serious Adverse Events** that are not Unanticipated Problems are submitted to the central IRB in the annual Continuing Review application. These events are officially reported to the Steering Committee at its monthly meeting and semi-annually to the DSMB.

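### Adverse-event counts by arm may differ through unequal ascertainment, because eight common research-assistant enquiries share one form with open reports from about 37 programme contacts in one arm and about 9 in the other

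*Combined protocol and SAP*

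**What the plan says.** Two routes lead to the same form.

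- **Scheduled route.** In Table 2 (Outcomes Assessment), the row "Vital Status, Adverse Events, Co-Interventions" is assigned to the RA at "3, PII, 9, 12, MM, 18, 21, EoT". That is five telephone contacts and three in-person visits. The stated goals of the in-person visits are to "collect follow-up data, update/confirm contact information, monitor adverse events, and promote retention". On visit timing the section says: "This timing applies to all participants, regardless of the treatment arm to which they were assigned". It makes the telephone schedule common to both arms as well.
- **Open route.** Safety Monitoring says: "All potential events reported by a participant or staff member are documented using the" Adverse Events Form. It does not distinguish events found by scheduled enquiry from events volunteered at other times.

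Contact with programme staff differs by design. In the Group-Based arm "meetings are held weekly for 3 months and bi-weekly for 3 months", and Table 1 numbers the last intensive session 19. Each session includes 20 minutes of physical activity. Monthly maintenance meetings, supported by the psychologist or the dietitian, run through months 7 to 24. In the Self-Directed arm there is one orientation meeting, and then "The Coordinator calls the participants every 3 months to answer questions about the trial and to enhance protocol adherence".

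Equipoise and Blinding keeps everyone except the interventionists blind to individual assignment. Trial Organization says that the data and safety monitoring board (DSMB) monitors data quality and safety, and that it "monitors outcomes by trial arm". The Analysis Plan contains no rule for summarising adverse events.

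**The concern.** The scheduled route is balanced between the arms and the open route is not. The additional Group-Based contacts are also with the only staff who know the assignment. A minor event, such as a strain or a fall without injury, has more chances to be mentioned in the Group-Based arm.

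If all reports are pooled, an excess in the Group-Based arm has two possible explanations, harm or closer contact, and the pooled data cannot separate them. A false signal could be raised. Equally, a real one could be dismissed as the result of closer contact. The matter is not purely cosmetic, because unexpected frequency is part of the plan's definition of an Unanticipated Problem. If the source of a report is not recorded when it is made, it cannot be reliably rebuilt later.

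The plan itself lists ascertainment bias among the hazards it wants to limit. The ongoing checks it names are crossovers, co-interventions and differential attrition. Detection of adverse events is not among them.

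**Working it through.** **1. Contacts at which adverse-event enquiry is scheduled (Table 2).** Months 3, 9, 12, 18 and 21 by telephone = 5, which agrees with the stated total of five telephone contacts. Adding PII, MM and EoT gives 5 + 3 = 8 in each arm, a ratio of 1.0.

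**2. Programme-staff contacts.**
- Group-Based, intensive phase: weekly for 3 months (13) + every two weeks for 3 months (6) = 19, which reproduces session 19 in Table 1.
- Group-Based, maintenance: monthly over months 7 to 24 = 18. Total 19 + 18 = 37.
- Self-Directed: 1 orientation + 24/3 = 8 calls = 9.
- Ratio 37/9 = 4.1. Including the eight RA contacts: (37 + 8)/(9 + 8) = 45/17 = 2.6.
- Sensitivity: at an assumed 80% attendance, 0.8 × 37/9 = 3.3. Meetings are offered at least twice a month, so if 36 maintenance meetings were attended the ratio would be 55/9 = 6.1.

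**3. From contacts to captured events.** The documents give no capture probabilities, so everything in this step is assumption. Take eight 3-month intervals with contacts spread evenly: 37/8 = 4.625 and 9/8 = 1.125 programme contacts per interval. Let s be the probability that the RA enquiry captures an event, and p the probability that one programme contact captures it, the same in both arms and independent between contacts. Then

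- Group-Based capture = 1 − (1 − s)(1 − p)^4.625
- Self-Directed capture = 1 − (1 − s)(1 − p)^1.125

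The apparent rate ratio under equal true rates is the first divided by the second. The table gives its maximum over all values of p.

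| RA recall s | p at maximum (about) | Group-Based | Self-Directed | Maximum ratio |
|---|---|---|---|---|
| 0.4 | 0.25 | 1 − 0.6 × 0.264 = 0.841 | 1 − 0.6 × 0.724 = 0.566 | 1.49 |
| 0.6 | 0.29 | 1 − 0.4 × 0.205 = 0.918 | 1 − 0.4 × 0.680 = 0.728 | 1.26 |
| 0.8 | 0.31 | 1 − 0.2 × 0.180 = 0.964 | 1 − 0.2 × 0.659 = 0.868 | 1.11 |
| 1.0 | any | 1.000 | 1.000 | 1.00 |

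At smaller p the ratio is lower. With p = 0.05 and s = 0.8 it is 0.842/0.811 = 1.04.

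**4. Early window.** Contacts are front-loaded: 19 against about 3 (orientation plus two calls) in the first 6 months, or 9.5 and 1.5 per interval. The same formula at s = 0.4 and p = 0.16 gives (1 − 0.6 × 0.191)/(1 − 0.6 × 0.770) = 0.886/0.538 = 1.65, the maximum for that recall. At s = 0.8 and p = 0.20 it gives (1 − 0.2 × 0.120)/(1 − 0.2 × 0.716) = 0.976/0.857 = 1.14. An early safety report could therefore show somewhat more imbalance than the 24-month total.

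**5. The scheduled route.** The text on telephone contacts gives their main purpose as vital status, health care utilization, co-interventions and contact details. It does not mention adverse events, although Table 2 does at the same five contacts. The completeness of five of the eight common enquiries, on which s depends, is therefore less clearly specified than Table 2 suggests.

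**The case against.** The strongest reply is that the plan already has a symmetric system: eight enquiries at the same times in both arms, by staff blind to assignment, followed by Site Physician adjudication and independent DSMB oversight. The fourfold figure counts contacts at which no adverse-event enquiry is scheduled. It also assumes full attendance, and it leaves out calls that Self-Directed participants may make to their Coordinator. This stands, and it is why the supportable word is may.

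Several stronger readings are tempting, and the documents do not support them.

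- **That event rates will differ through ascertainment alone.** If the RA enquiry is complete, the ratio is 1.0 whatever the number of programme contacts.
- **That 60% RA recall implies a ratio of about 1.7 (1.25 to 2.5 for recall of 80% to 40%).** These figures are 1/0.6, 1/0.8 and 1/0.4. They require full capture in the Group-Based arm and no capture at all from the nine Self-Directed contacts. Nothing in the plan supports that asymmetry.
- **That the form has no source field.** The form is not reproduced and part of the reporting process is in a figure not shown. A field may already exist.
- **That a planned by-arm comparison is invalid.** No adverse-event test is planned. The phrase "monitors outcomes by trial arm" refers to outcomes, with safety named separately in the same sentence. By-arm safety review is likely, but its format is not given.

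It can also be said that unequal contact is intended, since the comparator was not designed to control for attention. That explains the imbalance but does not help in interpreting the counts. Finally, restricting the by-arm comparison to RA-elicited events would sideline injuries reported at sessions, which are among the most direct possible harms of the programme. That objection is sound, so both displays are needed.

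**Conclusion.** The concern holds in a limited form. Pooled counts of non-serious events may differ by arm through ascertainment, and the plan states no means of telling this apart from a true difference. The contact imbalance is well established at about 37 to 9. Its effect on event counts is not. With equal, independent capture per programme contact, the scheduled number of contacts spread evenly and equal true rates, the apparent 24-month ratio is at most about 1.5 at 40% RA recall, 1.26 at 60% and 1.1 at 80%. It is 1.0 at complete recall. More meetings attended, or better detection at a group session than on a coordinator call, would raise these limits; lower attendance would reduce them.

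Deaths and hospital admissions are unlikely to depend on attendance at group sessions. The primary analysis of remission is unaffected. What is at stake is the interpretation of descriptive and DSMB safety summaries, and the remedy is cheap enough to be worth making.

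**What to change.** 1. Record the source of first report on the Adverse Events Form, if it is not already there: scheduled RA contact, programme session or coordinator call, or other.
2. Have the RA ask about all events at each of the eight common contacts, whether or not already reported, and without being prompted by session reports, so that the blind is kept. Align the stated purpose of the telephone contacts with Table 2.
3. In DSMB and final safety summaries, show two displays by arm: (a) all events, with session-reported events identified; and (b) events elicited at the eight common contacts plus all deaths and hospital admissions. Neither replaces the other.

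Expedited reporting is unchanged and no event goes unreported. The cost is one form field, some reconciliation of duplicate reports and a second safety display.
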